2.4.5.3 Deaths

The following summaries of deaths will be generated for the safety population.

- Number (%) of patients who died by study period (on-study, on-treatment, poststudy).
- TEAEs leading to death (death as an outcome on the adverse event case report form page as reported by the Investigator) by primary SOC and PT showing number (%) of patients sorted by internationally agreed SOC order and by decreasing incidence of PTs in the Toujeo treatment arm within each SOC. In case of a low number of events, only a listing will be provided.

Deaths in non-randomized patients or randomized but not treated patients will be also presented.

2.4.5.4 Analyses of laboratory variables

As most of safety laboratory parameters are only collected at screening and not during the study (see Section 2.1.4.3), no analyses will be performed.

2.4.5.5 Analyses of vital sign variables

The summary statistics (including number, mean, median, Q1, Q3, standard deviation, minimum and maximum) of all vital signs variables as well as changes from baseline will be calculated for each study assessment (baseline, Week 8 and Week 12, see Section 2.5.4) by treatment group.

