1.3 SCHEDULE OF ACTIVITIES (SOA)

	Screening (weeks)	F	Run-in	(weeks	Intervention period (weeks)														Follow up	Notes	
Procedure	-6/-5	-4	-3	-2	-1		1	2	3	4	5	6	7	8	9	10	11	12	EOTC	2 to 4 days after last IMP dose	Visit Windows: Site visits: ±3 days Phone call visits: ±1 day relative to Visit 6
Visit ^a	1	2	3	4 2	5 2	6	7 2	8	9	10	11	12 2	13 2	14	15	16 2	17 2	18 ^b		19 ^d	
Day	-42/-35	-28	-20	-14	-7	1	7	14	21	28	35	42	48	56	64	71	78	84		86-88	
Informed consent	Х																				To be repeated in case of rescreening
Inclusion/Exclusion criteria	Х	Х	Х			Х															
Demography	Х																				
Full physical examination including height and weight	Х																				
Medical history	Х																				Medical, surgical and diabetes history
Method of mealtime insulin titration	Х					х															Current method at screening and the one to be followed during treatment period at randomization
Vital signs and body weight	Х					х								Х				х	х		Vital signs include heart rate and blood pressure (sitting position)
Dispensation/collection of study diary		Χ	Х			Х								Х	Х			Х	Х		

	Screening (weeks)					lr	nterve	entio	n per	riod (v	veeks)				Follow up	Notes				
Procedure	-6/-5	-4	-3	-2	-1		1	2	3	4	5	6	7	8	9	10	11	12	EOT ^C	2 to 4 days after last IMP dose	Visit Windows: Site visits: ±3 days Phone call visits: ±1 day relative to Visit 6
Visit ^a	1	2	3	4 2	5 2	6	7 2	8	9	10 2	11	12 2	13	14	15	16 2	17 2	18 ^b		19 ^d	
Day	-42/-35	-28	-20	-14	-7	1	7	14	21	28	35	42	48	56	64	71	78	84		86-88	
Dispensation of study intervention						Х								Х							
IMP compliance check														Х				Х	х		Collecting and counting used and unused pens
IRT call ^e	Х					Х								Х				Х	Х		
Randomization						Х															
Documentation and review of basal and mealtime insulin dose	Х	Х	Х			х	Х	Х	Х	Х	Х	Х	Х	Х	Х	х	х	Х	х		
Prior and concomitant medication	Х	Х	Х			Х					и			Х				Х	Х	Х	
CGM device dispensation ; blinded CGM and training including insertion of CGM sensor			X												х				х		If required, Investigators can arrange for patient's to attend the site after the first 10 days of CGM for the sensor to be replaced at the study site.
CGM recording ^f				20days											2	20 days	s	Х			

	Screening (weeks)	I	Run-in	(weeks	s)					lr	nterve	entio	n per	riod (v	veeks	s)				Follow up	Notes
Procedure	-6/-5	-4	-3	-2	-1		1	2	3	4	5	6	7	8	9	10	11	12	EOTC	2 to 4 days after last IMP dose	Visit Windows: Site visits: ±3 days Phone call visits: ±1 day relative to Visit 6

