- a Telephone calls to monitor insulin titration should be scheduled by the Investigator for Weekly in between of site visits for all patients, unless the patient is attending the study site for sensor replacement. Option to come to site on D-10 and D74 for sensor replacement.
- b Visit 18 will occur at Week 12 regardless of the treatment end date, and procedures ticked below should be done
- c EOT (End Of Treatment) visit will occur in case of premature discontinuation of study treatment before Visit 18 at week 12 and related procedures ticked below should be applied. If at the time of such premature discontinuation there is ongoing CGM recording, it should be completed, and EoT vist done thereafter. Afterward, the patients should continue in the study up to the scheduled date of study completion. See Section 7.1
- d If EOT visit occurs beyond 2 to 4 days after last administration of study drug then Visit 8 will not be required. EOT and safety follow up can be done at the same time, if occurs within 2 to 4 days after last IMP dose.
- e The Investigator should contact IRT either at Visit 18 or at EOT visit in case of premature end of treatment (whichever occurs first), to register end of treatment.
- f For each 20 day CGM period to be fully evaluable for CGM it is necessary to obtain a minimum of 10 days (not necessarily consecutive) of useable CGM data. Useable CGM data for a day/a 24-hour CGM profile are defined as: at least 80% time of records per 24 hours; no gap (missing data) lasting for ≥2 hours per 24 hours besides the warm-up time for the sensor after insertion.
- g SMPG to be performed by the patients from run-in period and throughout the study duration:
 - 1. Fasting (pre-breakfast/pre-injection) SMPG: daily until dose stabilization of basal insulin has been completed and fasting SMPG goal is reached. Thereafter, the number of fasting SMPG checks can be reduced according to the Investigator's judgment, however at least 3 fasting (pre-breakfast) SMPG measurements per week should be done.
 - 2. SMPG values throughout the study, starting after Visit 2. Patients should test their SMPG following the Investigator's instructions for mealtime insulin titration.
 - 3. 2hPPG (post prandial plasma glucose); regularly as instructed by investigator to guide meal time insulin titration;

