2.1.4 Safety endpoints

To address the secondary objective of evaluating the safety of insulin glargine 300 IU/mL in comparison to insulin degludec 100 IU/mL, the following endpoints will be observed

- Number of patients with adverse events (see Section 8.3 of the protocol).
- Number of patients with at least one hypoglycemic event from baseline to Week 12.
- Number of hypoglycemic events per participant-year from baseline to Week 12.

The safety analysis will be based on the reported adverse events (AEs) and other safety information, such as vital signs. The specific safety parameter of interest for insulin treatment is hypoglycemia.

Observation period

For all safety data, the observation period will be divided as follows:

- The pre-treatment phase is defined as the time from when the patients sign the informed consent to first injection of IMP (excluded).
- The on-treatment phase is defined as the time from the first injection of IMP (included) up to 2 days after the last injection of IMP.
- The post-treatment phase is defined as the time after the on-treatment phase until the end of the study (Follow up Visit).

On-study observation period is defined as the time from start of treatment until the end of the study (defined as last protocol planned visit or the resolution/stabilization of all serious adverse events (SAEs) and AEs of specific interest (AESI) as defined in the protocol).

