2.1.4.4 Vital signs variables

Vital signs will be assessed according to the defined visit window (see Section 2.5.4).

The following vital signs will be assessed:

- Weight (Kg),
- Systolic blood pressure (mmHg) in sitting position,
- Diastolic blood pressure (mmHg) in sitting position,
- Heart rate (beats/min) in sitting position.

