2.5.4 Windows for time points

The windows below will be employed for the main primary and secondary efficacy endpoints as well as vital sign which will also be collected during the study for both scheduled and unscheduled visits.

CGM

CGM values measured outside the visit window will be flagged for exclusion from analyses. No derivations of CGM endpoints will be performed for CGM data collected outside of the analysis CGM window. Study days for CGM evaluations are calculated from the randomization date, and Day 1 indicates the day of randomization.

	Target CGM visit in Study day	Analysis CGM window in study day
CGM study visit		
Week- 3 to Week -1	Day -20 to Day -1	-28 to -1
Week 10 to Week 12	Day 64 to 84	57 to 91

For 7-point SMPG, HbA1c, FPG and PROs: Day indicates days relative to randomization date, and Day 1 indicates the day of randomization.

7-point SMPG

	Target Study day	Analysis window in study day	
Time point			
Week 12	84	77 to 91	
HbA1c, FPG			
	Targeted Study Day	Analysis window in study days	
Time Point			
Week 12	84	77 to 91	

PROs

	Targeted Study Day	Analysis window in study days
Time Point		
Week 12	84	77 to 91

Vital signs - Safety

Study days for vital signs evaluations are calculated from the day of first IMP injection, the day of first IMP injection being Day 1. The last assessment before the first study drug intake will be considered as Baseline.

	Target visit in Study day	Analysis window in study day
Time Point		
Week 8	56	49 to 63
Week 12	84	77 to 91

One or more results for a required parameter may be recorded within a given visit window. In such an event, the assessment with the closest date to the scheduled visit date will be used. In the event of 2 observations within a given visit window being equidistant to the scheduled visit date, the first observation will be used for descriptive tabulations or figures.

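### The vital-sign and body-weight summaries do not apply the SAP's own on-treatment phase, so off-drug Week 8 and Week 12 readings count under the stopped insulin and some end-of-treatment readings enter no summary

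*SAP*

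**What the plan says.** The protocol's schedule of activities (Section 1.3) has a row for "Vital signs and body weight", ticked at Visits 1, 6, 14 (Week 8) and 18 (Week 12) and at EOT. Note c states that the "EOT (End Of Treatment) visit will occur in case of premature discontinuation of study treatment before Visit 18 at week 12". It adds that EOT waits if a CGM recording is running, and that the patient then stays in the study. Note b adds that "Visit 18 will occur at Week 12 regardless of the treatment end date".

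SAP 2.4.5.5 summarises vital signs and their changes from baseline, which "will be calculated for each study assessment (baseline, Week 8 and Week 12, see Section 2.5.4) by treatment group". SAP 2.1.4.4 lists weight among these variables. SAP 2.5.4 sets the windows at Day 49-63 and Day 77-91: "Study days for vital signs evaluations are calculated from the day of first IMP injection". If a window holds several readings, "the assessment with the closest date to the scheduled visit date will be used".

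SAP 2.1.4 introduces the pre-, on- and post-treatment phases with "For all safety data, the observation period will be divided as follows". The on-treatment phase runs from the first injection to 2 days after the last. SAP 2.4.5 assigns each patient to the treatment actually received.

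**The concern.** Two things follow from the wording. A patient who stops the insulin early but attends Visit 18 contributes a Week 12 reading taken off that insulin, and the table counts it under that insulin. A patient who stops before Visit 14 can do the same in the Week 8 row. Second, the EOT reading taken when treatment ended early is summarised only if its date happens to fall in one of the two windows.

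Other safety outputs follow the phase definition: treatment-emergent adverse events (SAP 2.1.4.1), on-treatment deaths (2.1.4.2), and hypoglycemia odds ratios and rate ratios (2.4.5.1). The vital-sign text does not mention it. At stake is whether the weight, blood pressure and heart rate table describes patients while on the two insulins. It is the only planned summary of post-baseline vital signs.

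**Working it through.** The plan gives no figure on this point to reproduce. The check counts days.

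**Inputs**
- Windows: Day 49-63 and Day 77-91, with Day 1 the first injection (SAP 2.5.4).
- On-treatment phase: to last injection + 2 days (SAP 2.1.4).
- Visit 18 at Day 84, and EOT before it, so possible stop days are Days 2-83: 83 − 2 + 1 = 82.
- Endpoint CGM recording: Days 64-84 (Protocol 8.1.1.1). Under note c, a stop in that period moves EOT to about Day 84.
- Rate and timing of discontinuation: not given. The 22% in the sample-size section is a non-evaluability rate for the CGM endpoint, so it does not supply them.

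**1. EOT on the stop day, even timing, no postponement.** Days inside a window: 15 (Days 49-63) + 7 (Days 77-83) = 22. Outside: 82 − 22 = 60, and 60/82 = 73%.

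**2. With the CGM postponement.** Stops on Days 64-83 now have EOT at about Day 84, inside the Week 12 window. Only Days 2-48 remain uncovered: 47/82 = 57%.

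**3. Other timings, with postponement.**
- Back-loaded (weight d on Day d): the sum over Days 2-48 is 48×49/2 − 1 = 1,175, and over Days 2-83 it is 83×84/2 − 1 = 3,485. The share is 1,175/3,485 = 34%. If EOT comes 3 days after the stop, the uncovered stop days are 2-45 (sum 1,034) and 61-63 (sum 186), giving 1,220/3,485 = 35%.
- Front-loaded (weight 84 − d): 2,773/3,403 = 81%.

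**4. Off-drug readings at Week 12.** With the last injection on day s, the Day 84 reading is post-treatment when s + 2 < 84, that is s ≤ 81. This holds for 80 of the 82 stop days. A stop on Day 48 ends the on-treatment phase on Day 50, so Day 84 is 34 days past it.

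**5. A tabulated EOT reading is not always on-treatment.** Of the 20 stop days 64-83 whose EOT is postponed to about Day 84, 18 (Days 64-81) give an EOT reading that is already post-treatment.

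**6. Patients, under an assumed 3% to 10% discontinuation.** 3% of 338 is 10.1 and 10% is 33.8. Untabulated EOT readings, both arms together:

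| Timing of stops | Share | Readings |
|---|---|---|
| Even, with postponement | 57% | about 6 to 19 |
| Even, without postponement | 73% | about 7 to 25 |
| Back-loaded, with postponement | 34% | about 3 to 11 |

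**7. Effect on the Week 12 mean.** If a share f of the row is off drug and those readings have lost the whole drug effect, the mean moves by f times that effect. At f = 3% to 10%, that is 3% to 10% of the effect. This is an upper bound, because it needs every early stopper to attend Visit 18 off drug.

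**The case against.** The strongest reply is that SAP 2.1.4 already divides all safety data by phase and names vital signs as safety information, so an on-treatment limit may be implied. That partly stands: the phase exists, and the gap is that the vital-sign sections do not apply it. SAP 2.4.5.1 does state the limit for hypoglycemia. Even if the limit is implied, EOT readings outside both windows still have no row.

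A by-visit table that follows patients after discontinuation is also a defensible choice. However, SAP 2.1.3 sets that rule for efficacy only, while safety is divided by treatment phase.

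A reader might infer three stronger things that the documents do not support:
- **That most EOT readings are lost.** This depends on when patients stop, which is not stated. It fails if stopping is back-loaded and EOT is postponed.
- **That the EOT reading is always the last one on the drug.** Note c can postpone it, and note d foresees EOT more than 2 to 4 days after the last dose.
- **That a safety problem would be hidden.** Vital signs and weight are not among the listed safety endpoints, and the analysis is essentially descriptive (SAP 2.4.5). Clinically significant vital-sign findings are adverse events (Protocol Appendix 3). Treatment-emergent events leading to discontinuation are tabulated (SAP 2.4.5.2). EOT readings also stay in the database; what they lack is a summary row.

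**Conclusion.** The point holds as a minor improvement. As written, Week 8 and Visit 18 readings taken more than 2 days after the last injection are counted under the stopped insulin. EOT readings outside Day 49-63 and Day 77-91 enter no summary. With even timing, the untabulated share of stop days is 57% with the CGM postponement and 73% without it; with back-loaded stopping and postponement it is about 34-35%. The timings and the 3-10% rate are assumptions. That a Day 84 reading is off drug after any stop before Day 82 follows from the SAP's own phase definition and needs no assumption about timing. The consequence is limited to one descriptive safety table. The primary analysis and the sample size are unaffected.

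**What to change.** In SAP 2.4.5.5 and 2.5.4:
- Restrict the post-baseline by-visit summaries of vital signs and weight, by date, to readings from the first injection to 2 days after the last. Make no exception for the EOT visit, since that would bring off-drug readings back in.
- Apply this restriction before choosing the reading closest to the scheduled date, so that an off-drug value cannot displace an on-treatment one.
- Add a row for the last on-treatment value with its change from baseline. Include an EOT reading only if its date falls within that period.
- Show later EOT and Visit 18 readings separately as post-treatment.

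The cost is a few lines of SAP text and some extra table rows from data already collected, with slightly fewer patients in the Week 8 and Week 12 rows. This changes tabulation only and touches no clinical management rule.

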2.4.5.6 Analyses of electrocardiogram variables

Not applicable to the study.

2.4.6 Analyses of pharmacokinetic and pharmacodynamic variables

Not applicable to the study

2.4.7 Analyses of quality of life/health economics variables

The analyses will be done on ITT population.

For DTSQs, MOS-Sleep, and WPAI, a descriptive summary of each score (see Section 2.1.7) will be done at baseline and at Week 12.

Change in DTSQs, MOS-Sleep, and WPAI scores from baseline to Week 12 will be analyzed using an ANCOVA model including the fixed categorical effects of treatment group (Toujeo, Tresiba), and the randomization stratum of HbA1c at screening (< 8.0%, $\geq 8.0\%$), as well as, the continuous fixed covariate of baseline score.

LS means and the corresponding SEs and 95% confidence interval by treatment for the change from baseline will be presented for descriptive purposes.

The DTSQc score will be analyzed using descriptive statistics at Week 12.

The DTSQc scores at Week 12 will be analyzed using an ANCOVA model including the fixed categorical effects of treatment group (Toujeo, Tresiba), DTSQs score at baseline, and the randomization stratum of HbA1c at screening (< 8.0%, $\geq 8.0\%$).

LS means differences in scores between treatment groups and its SEs and their corresponding 95% confidence interval of will also be evaluated.

2.5 DATA HANDLING CONVENTIONS

The following formulas will be used for computation of parameters:

2.5.1 General conventions

CGM days will be defined as starting/ending at 00:00/23:59 on the 24-hour clock. Only useable CGM days within the time windows (see Section 2.5.4) are used for derivation of CGM endpoints (primary and secondary).

Percentage time in range

The proportion of CGM readings falling into the range of \geq 70 to \leq 180 mg/dL [\geq 3.9 to \leq 10 mmol/L] from useable CGM (at least 10 useable days among the 20-day CGM within the time-window, see Section 2.5.4).

If there is missing data between two available measurements, linear interpolation will be performed to impute the time points with missing data. For example, if a glucose value is less than 70 mg/dL at 5 min, missing at 10 and 15 min then higher than 180 mg/dL at 20 min, the data at 10 and 15 minutes will be imputed using linear interpolation. Missing data at the start of the day and end of day will not be imputed.

Demographic formulas

- If the date of T1DM diagnosis is not missing, age at diagnosis will be calculated extracting the year from the date of the T1DM diagnosis and the year of birth:
 - a) Age at diagnosis (years) = YEAR (date of diagnosis) year of birth.
- Time since diabetes diagnosis will be derived:
 - a) Time since diabetes diagnosis (years) = Integer [(date of Informed Consent Date of Diagnosis + 1)/365.25].

Disease characteristics at baseline formulas

• Total daily insulin dose adjusted for body weight: Total daily dose (IU) / body weight in kg.

Physical examination formulas

- BMI (Quetelet index formula):
 - a) Weight (kg) / (Height (m) × Height (m))

where using height assessed at Screening Visit and body weight collected over the study.

2.5.2 Data handling conventions for secondary efficacy variables

2.5.2.1 CGM secondary and tertiary endpoints

• mean hours per day = percent time × 24 hours

24-hour Area under the Curve (AUC24), derived using the trapezoidal rule based on AUCt (AUC over the CGM assessment period) and then divided by the number of days with usable CGM data. Trapezoidal rule:

a) $0.5 \times ($ glucose reading at time i + glucose reading at time i-1 $) \times ($ time i - time i-1).

Note: Missing values for calculation of AUC will be treated as not collected.

The following main secondary endpoints will be calculated as follows:

• Glucose total CV = 100% times square root of s_{total}^2 divided by the mean glucose \bar{y} . That is:

$$CV_{total} = 100 \times \frac{s_{total}^2}{\bar{y}}$$

with

$$s_{total}^{2} = \frac{\sum_{i=1}^{k} \sum_{j=1}^{n_{i}} (y_{ij} - \bar{y})^{2}}{N - 1}$$

and

$$ar{y} = rac{\sum_{i=1}^k \sum_{j=1}^{n_i} y_{ij}}{N}$$
 ,

where N is the number of total useable CGM data for each patient; k is the number of CGM assessment days; y_{ij} is the j^{th} CGM data from the Day i and n_i is the number of total useable CGM data within the Day i.

• Glucose between days CV = 100% times square root of $s^2_{between}$ divided by the mean glucose \overline{y} . That is:

$$CV_{between} = 100 \times \frac{s_{between}^2}{\bar{y}}$$

with

$$s^{2}_{between} = \frac{\sum_{i=1}^{k} (\bar{y}_{i} - \bar{y})^{2}}{K - 1}$$

where \bar{y}_i is the mean glucose for Day *i*:

$$\bar{y}_i = \frac{\sum_{j=1}^{n_i} y_{ij}}{n_i}.$$

Property of the Sanofi Group - strictly confidential

Page 39

VV-CLIN-0612739 1.0

01-Jul-2021 Version number: 1

• Glucose within days CV = 100% times square root of s^2_{within} divided by the mean glucose \overline{y} . That is:

$$CV_{within} = 100 \times \frac{s_{within}^2}{\bar{y}}$$

with

$$s^{2}_{within} = \frac{1}{K} \sum_{i=1}^{k} \frac{\sum_{j=1}^{n_{i}} (y_{ij} - \bar{y}_{i})^{2}}{n_{i} - 1}.$$

A Proc Varcomp procedure will be used to compute Glucose within days CV and Glucose between days CV for each patient where time point variability within each day is also accounted for

```
proc varcomp data =dsn;
by USUBJID avisit;
class ADY TIMEBIN;
model AVAL = ADY TIMEBIN;
ods output estimates=outstat;
run;
```

where:

AVAL: glucose value AVISIT: Analysis visit including Baseline and Week 12 ADY: Analysis day TIMEBIN: Timepoints

The CGM secondary/exploratory endpoints related to percent in time in range whatever the threshold(s) will be derived on a similar way as the primary endpoint.

• GMI (%) = $3.31 + 0.02392 \times (\text{mean glucose in mg/dL})$

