2.1.3 Efficacy endpoints

Observation period for efficacy endpoints

The 12–week randomized period for efficacy variables is defined as the time from randomization until Week 12 (Visit 18) for randomized patients, regardless of study treatment discontinuation.

CGM data

A patient is eligible for randomization if a minimum of 10 days (not necessarily consecutive) of useable CGM data are generated during 20 consecutive days at run-in period.

At Week 12, CGM is evaluable if there is at least 10 days of useable CGM data (not necessarily consecutives) within the analysis time windows (see Section 2.5.4) at Week 12 evaluation.

Useable CGM data for a day/a 24-hour CGM profile are defined as having:

- At least 80% time of records per 24 hours (ie, 231 data points among the 288 recorded in 24 hours).
- No gap (missing data) lasting for a total of ≥ 2 hours per 24 hours besides the warm-up time for the sensor after insertion.

For CGM endpoints, details on derivations are available in Section 2.5.

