2.1.3.2 Secondary efficacy endpoint(s)

To address the secondary objective of evaluating the glycemic control and variability parameters in each treatment group, efficacy endpoints will be assessed using CGM, HbA1c, and FPG.

At Week 12 the following main secondary endpoints will be assessed using CGM (see Section 2.5.2.1).

- Glucose total coefficient of variation (CV) (%), main secondary endpoint,
- Glucose within-day and between-day CV (%).

Other secondary endpoints to be assessed are:

Based on central lab

- Change from baseline to Week 12 in HbA1c (% and mmol/mol),
- Change from baseline to Week 12 in FPG (mmol/L and mg/dL).

Based on CGM

- Percent time and mean hours per day with glucose <70 mg/dL (on all time [00:00 to 23:59] and during the night [00:00 to 5:59] obtained from CGM,
- Percent time and mean hours per day with glucose >180 mg/dL obtained from CGM.

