2.1.3.3 Tertiary/exploratory efficacy endpoint(s)

To address the tertiary objective of exploring the glycemic control and variability parameters in each treatment group at Week 12 using CGM, the following endpoints will be assessed:

- Mean hours per day in the glucose range of \geq 70 to \leq 180 mg/dL (\geq 3.9 to \leq 10 mmol/L),
- Percent time and mean hours per day in the glucose range of \geq 70 to \leq 140 mg/dL (\geq 3.9 to \leq 7.8 mmol/L) (on all-time and during the night [00:00 to 05:59]),
- Nocturnal [00:00 to 05:59] percent time in glucose range of \geq 70 to \leq 180 mg/dL (\geq 3.9 to \leq 10 mmol/L),
- Day time [06:00 to 23:59] percent time in glucose range of ≥70 to ≤180 mg/dL (≥3.9 to ≤10 mmol/L),
- Percent time and mean hours per day with glucose <54 mg/dL (<3.0 mmol/L) (on all time and during the night [00:00 to 5:59]),

- Percent time with glucose <70 mg/dL (<3.9 mmol/L) within the 12 hours after basal insulin injection,
- Percent time and mean hours per day with glucose >250 mg/dL (>13.9 mmol/L),
- Mean glucose profile over a 24-hour period,
- 24-hour Glucose Area Under the Curve (AUC mg/dL*minutes), derived using the trapezoidal rule. The derivation will be adjusted to be an hourly average (Section 2.5.2.1),
- Mean glucose,
- GMI,
- Percent time and mean hours per day in the glucose range of ≥54 to <70 mg/dL (≥3.0 to <3.9 mmol/L) (on all-time and during the night [00:00 to 05:59]),
- Percent time and mean hours per day in the glucose range of >180 to $\leq 250 \text{ mg/dL}$ (>10 to $\leq 13.9 \text{ mmol/L}$) (on all-time and during the night [00:00 to 05:59]).

Other tertiary/exploratory endpoints than those related to CGM:

- Daily insulin doses (total daily insulin, basal insulin, mealtime insulin, ratio of basal to mealtime insulin dose) in units and U/kg body weight at each visit. Change at Week 8 and Week 12 from baseline will be derived.
- Change from baseline to Week 12 in patient-reported outcomes (treatment satisfaction, sleep quality and quantity, and productivity) (for detail on PROs, see Section 2.1.7).
- 7-point SMPG profiles (pre-prandial and 2-hour postprandial plasma glucose at breakfast, lunch, dinner, and bedtime) at Week 12 and change in 7-point SMPG profiles from baseline to Week 12.

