2.4.4.2.1 CGM secondary endpoints

The CGM endpoints will be analyzed using an ANCOVA model

- Glucose total CV (main secondary endpoint)
- Glucose within-day and between-day CV
- Percent time and mean hours per day with glucose <70 mg/dL (on all time and during the night [00:00 to 05:59])
- Percent time and mean hours per day with glucose >180 mg/dL

The ANCOVA model to perform the analysis includes the fixed categorical effects of treatment group (Toujeo, Tresiba), randomization stratum of screening HbA1c (< 8.0% versus $\geq 8.0\%$), as well as the continuous fixed covariate of baseline value for the corresponding endpoints.

For glucose total CV (main secondary endpoint), and if the non-inferiority on the primary endpoint is demonstrated, the non-inferiority will be tested. But, unlike TIR, for CV the lower the better. Therefore, the non-inf comparison will be based on:

H0: m1 - 1.1 × m0 \ge 0

For the other secondary endpoints, LSmeans treatment difference (with the corresponding SEs and 95% CI) will be provided and the p-value (of the difference between the two treatments) will be provided for descriptive purpose only (see Section 2.4.4.4).

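### The SAP's single × 24 rule for mean hours per day has no version for the 6-hour night window, so on the natural reading five night-hours endpoints come out 4 times too large

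*SAP*

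**What the plan says.** SAP Section 2.5 presents its formulas as those to be used for computing the parameters. Under Section 2.5.2.1, which covers the CGM secondary and tertiary endpoints, the only conversion from percent to hours is "mean hours per day = percent time × 24 hours".

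Section 2.1.3.2 lists as a secondary endpoint "Percent time and mean hours per day with glucose <70 mg/dL (on all time [00:00 to 23:59] and during the night [00:00 to 5:59" (the night window closes the bracket). Section 2.1.3.3 asks for mean hours per day during the night for four more ranges: 70–140, <54, 54 to <70, and >180 to 250 mg/dL.

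For the denominator, Section 2.5.1 defines percent time in range for the primary endpoint as "The proportion of CGM readings falling into the range of" 70–180 mg/dL on useable days. Section 2.5.2.1 adds that the other percent-time endpoints, whatever their thresholds, "will be derived on a similar way as the primary endpoint". That sentence covers thresholds. It does not cover time windows shorter than a day.

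**The concern.** A 24-hour multiplier converts a share of the day into hours. Applied to a share of a 6-hour window, it gives a figure 4 times too large. The SAP makes no exception for the night, and its text leaves the night denominator unwritten.

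The secondary endpoint is the one that matters most. Section 2.4.4.2.1 reports least-squares means and a treatment difference with SE and 95% CI for night hours below 70 mg/dL. Protocol Section 3.1 expects less night-time hypoglycemia with Toujeo, so readers will look at this result. Hours are also the unit that a clinician reads directly, and at low percentages an inflated value would not look impossible.

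**Working it through.** **Inputs**
- Readings per day: 288, from SAP Section 2.1.3 ("231 data points among the 288 recorded in 24 hours"), which is one every 5 minutes.
- Night window: 00:00 to 05:59, 6 hours (SAP Sections 2.1.3.2 and 2.1.3.3).
- Conversion: percent time × 24 hours (SAP Section 2.5.2.1), with percent taken as a proportion, so 5% = 0.05.

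**Step 1. The rule works for the whole day.** For k readings in range, k/288 × 24 h should equal k × 5 min. With k = 144, 144/288 × 24 = 12.0 h and 144 × 5 min = 12.0 h. With k = 12, both give 1.0 h. The all-time endpoints are correct.

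**Step 2. The night window.** It holds 288 × 6/24 = 72 readings. Take 4 night readings below 70 mg/dL, which is 4 × 5 = 20 min = 0.33 h.

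| Denominator | Night percent time | × 24 | × 6 |
|---|---|---|---|
| A: 72 night readings | 4/72 = 5.56% | 1.33 h | 0.33 h |
| B: 288 readings of the day | 4/288 = 1.39% | 0.33 h | not applicable |

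Under A the × 24 rule is wrong by 24/6 = 288/72 = 4. Under B it is right.

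**Step 3. Which denominator is meant?** On a complete day, B would cap three kinds of percentage in Section 2.1.3.3:
- Night percentages: 72/288 = 25%. A patient in range all night would be reported as 25%.
- The daytime endpoint ("Day time [06:00 to 23:59] percent time in glucose range of" 70–180 mg/dL): 216/288 = 75%.
- Percent time below 70 mg/dL "within the 12 hours after basal insulin injection": 144/288 = 50%.

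These caps make A the natural reading.

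**Step 4. Size under A.** The documents give no night percentages, so these are assumed values.

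| Assumed night percent time | × 24 as written | × 6 correct |
|---|---|---|
| 2% | 0.48 h | 0.12 h |
| 5% | 1.20 h | 0.30 h |
| 8% | 1.92 h | 0.48 h |
| 25% | 6.0 h | 1.5 h |
| 50% | 12.0 h | 3.0 h |

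Reported night hours exceed the 6-hour window once night percent time is above 6/24 = 25%, which is most plausible for 70–140 mg/dL. They exceed the all-day hours for the same threshold whenever night percent time is above all-time percent time, which is impossible for true hours.

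**Step 5. Effect on the model.** Using × 24 in place of × 6 multiplies both the outcome and the baseline covariate by 4. The baseline slope is unchanged. The treatment difference, its SE and both CI limits are multiplied by 4. Their ratio, t, and the p-value stay the same.

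**Step 6. Count.** Five endpoints have a night-hours version: <70 (secondary), and 70–140, <54, 54 to <70 and >180 to 250 mg/dL (exploratory). The night and daytime 70–180 mg/dL endpoints and the 12-hour post-injection endpoint are percent only. The hours endpoints for 70–180, >180 and >250 mg/dL have no night version.

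**The case against.** The strongest reply is that this is an undefined denominator and not a wrong number. Section 2.5.1 works with whole calendar days. If the other endpoints follow it literally, the denominator is every reading on the useable days, and × 24 is then exact. The case for night readings rests on plausibility, since no sentence in the SAP says so. The line may also be shorthand: on a 0–100 scale it needs a division by 100 that is not printed, so a sensible programmer might also replace 24 by the window length.

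It is true that the factor of 4 is conditional and that the program cannot be seen. But the whole-day denominator does not rescue the plan. It makes the hours right only by giving night, daytime and post-injection percentages an unusual and unstated ceiling. One written rule cannot yield both sensible night percentages and correct night hours. Reading 5% as 0.05 is ordinary notation, whereas using 6 where the SAP prints 24 departs from the rule.

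The reply is also right that the impact is small. Four of the five endpoints are summarized descriptively. The fifth lies outside the testing hierarchy, and for it "the p-value (of the difference between the two treatments) will be provided for descriptive purpose only". Percent time is reported beside the hours.

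**Conclusion.** The conversion rule is wrong as written for the night window. The size is a factor of exactly 4 if night percent time is a share of night readings, and 1 if it is a share of all readings in the day. The first reading is an inference from the 25%, 75% and 50% ceilings, because the SAP does not state the denominator.

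The damage is confined to the reported hours: the least-squares means, difference, SE and CI for night hours below 70 mg/dL, and four exploratory summaries. The primary endpoint, glucose total CV, the testing hierarchy, the percent-time endpoints and all p-values are untouched. So are the hypoglycemia event analyses, because SAP Section 2.1.4.6 excludes CGM values from them. It should still be corrected, because two programmers following this text could produce results that differ fourfold.

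**What to change.** Replace the line in SAP Section 2.5.2.1 with: mean hours per day = (percent time/100) × window length, where the window length is 24 h for all time and 6 h for 00:00–05:59. State in the same place that the denominator of percent time is the readings inside that window on useable days. Apply the same denominator wording to the daytime and 12-hour post-injection percentages.

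The cost is one line in the SAP and a matching change in the derivation program. It needs no new data and alters no confirmatory analysis.
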